Aim 2: To examine the effect of a physical therapist led physical activity intervention on the changes in physical activity, physical function, and pain in TKR patients.

4) Setting

The study procedures will be performed at Palmetto Health USC Orthopedic Centers. Potential patients will be identified and recruited after they attend their first physical therapy appointment by physical therapists participating in the study. Patients who are interested in participating will complete the informed consent process with the Principal Investigator or study research assistants. Study data and consent forms will be stored in a locked office at Palmetto Health USC Orthopedic Centers and the University of South Carolina Technology Center to Promote Healthy Lifestyles.

5) Resources Available

The purpose of this study is to examine the feasibility of conducting a physical therapist led physical activity intervention in a clinical setting. We will strive to recruit a total of 50 patients. If recruitment efforts are slow, we will plan to recruit additional physical therapists to participate in the study and assist with recruitment over the 15 month granted funded period of time.

[name], the Principal Investigator and Assistant Professor in the Department of Exercise Science at USC, will oversee all study related procedures, included but not limited to recruitment, behavioral intervention, and data collection and analysis. [name] has extensive experience overseeing behavioral clinical trials.

[name], Co-Investigator and Senior Physical Therapist, will help recruit patients at Palmetto Health USC Orthopedic Centers and will coach participants as part of the intervention during standard physical therapy appointments.

[name], Co-Investigator and Clinical Psychologist, will serve as the mentor to [name] as well as oversee delivery and treatment fidelity of the behavioral intervention. Additionally, [name] serves as a PI for another study through Palmetto Health (Pro00033131 Promoting Health in Pregnancy and Postpartum).

All members of the study team will have a copy of the study protocol and know their respective research duties.

6) Prior Approvals

NA

7) Study Design

a. Recruitment Methods

Patients will be recruited from Palmetto Health USC Orthopedic Center. After completing the first outpatient physical therapy appointment, potentially eligible patients

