Assessments will be completed before the second outpatient therapy session (baseline) and at 12 weeks after TKR. Detailed descriptions and a timeline of outcomes are provided below in the text and Table 2. Briefly, at both assessments, participants will be asked to complete surveys (demographics, brief medical history, KOOS, PROMIS, self-identification), which should take approximately 20 minutes to complete. Based on participant preferences, surveys will be able to be completed on paper or online via RedCAP, with the exception of the PROMIS surveys which are computer adaptive surveys. Participants will also be given an Actigraph Link accelerometer and ActivPAL monitor to wear for 7 days at each assessment. These monitors will be provided at the in-person assessment or mailed to the participants. At the end of the 7 days, these monitors will be returned to the PT clinic or participants will be provided with a prepaid padded envelope to return the monitor. Only at 12 weeks will participants complete functional tests and the Surgery and Medication Questionnaire, which will take approximately 15 minutes to complete. In the event participants are unable to complete the function tests at the in-person assessment, we will ask participants to complete the chair stand test at home and self-report the outcomes. Participants will not be asked to complete the 6-minute walk or timed up and go at home. Participants will receive \$20 for completing the 12-week assessment.

Measure	Baseline	12 Weeks
Participant Demographics	X	
Participant height and weight	X	X
Brief Medical History	X	X
Knee Injury and Osteoarthritis Outcome Score (KOOS)	X	X
PROMIS Pain Intensity, Pain Interference, & Mobility	X	X
WOMAC Pain and Stiffness	X	X
Physical Function		
6-minute walk		X
Timed up and go		X
Chair stands		X
Physical activity (Actigraph)	X	X
Sedentary time (ActivPAL)	X	X
Self-Reported Exercise Identity	X	X
PATH Study Survey		X

Primary Outcomes: The feasibility and acceptability of conducting a randomized controlled trial within an outpatient physical therapy setting is the primary endpoint. Specifically, we will examine the number of participants enrolled vs. approached, participant retention, number of therapy sessions attended, session duration, and treatment fidelity. Further, participants will complete a PATH Study Survey at the 12 week assessment. Physical therapists will complete a brief evaluation about delivering the PATH program.

Secondary Outcomes:

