- Physical activity will be measured using Actigraph Link accelerometers owned by the TecHealth Center at the University of South Carolina. During assessments, participants will be asked to wear the Actigraph on their waist for 7 days. Non-wear time will be defined as ≥ 90 minutes with zero activity counts, allowing for up to 2 minutes of <100 counts/min.²⁶ Physical activity will be categorized as light (100-2019 counts/min) and moderate-to-vigorous (MVPA) (≥ 2020 counts/min).²⁷ Total MVPA over the week will be calculated. Steps/day will also be obtained. A valid day will be considered if participants wore the accelerometer for at least 10 hours/day. Participants will also be asked to complete a log indicating times the accelerometer was worn and taken off over the 7-day assessment period.
- Sedentary time will be measured using ActivPAL™ (PAL Technologies Ltd, Glasgow, UK), a small lightweight (15 g) uni-axial accelerometer. The time spent sitting/lying, standing, and walking, transitions and step counts will be determined. The ActivPAL summarizes data in 15 second intervals over 24 hours at a sampling frequency of 10 Hz.²⁸ During assessments, participants will be asked to wear the ActivPAL on their thigh for 7 days. Participants will also be asked to complete a log indicating times the ActivPAL was worn and taken off over the 7-day assessment period.
- Physical function measures will include the chair stand, timed up and go, and 6-minute walk test. All physical function tests will be completed following Osteoarthritis Research Society International (OARSI) recommendation procedures.²⁹ During the chair stand test, patients are asked to complete as many chair stand repetitions as possible during a 30-second period. The Timed Up and Go Test assesses the time in seconds taken to rise from a chair, walk 3-meters, turn, walk back to the chair, and sit down. The Six Minute Walk Test evaluates the maximal distance a patient can cover during a 6-minute period.
- Patient-Reported Outcomes will be assessed using two methods: 1) Patient-Reported Outcomes Measurement Information System (PROMIS)³⁰ utilizes a computer adaptive test via RedCap.³¹ We will assess pain intensity, pain interference, and mobility; 2) Western Ontario and McMaster Universities Arthritis Index (WOMAC) is a 15-item survey assessing pain and stiffness over the last 48-hour on a 5-point Likert scale.³²

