Treatment Fidelity. Due to the open, group-like nature of physical therapy and patient confidentiality, we are unable to audio record treatment sessions. Therefore, to monitor treatment fidelity to ensure intended session content for both conditions is delivered and that unintended session content (i.e., contamination such as goal setting on physical activity levels with a patient randomized to PATH-12) is not delivered, physical therapists will complete a session checklist. In addition, random observations will occur by USC research staff. The physical therapist and observation fidelity checklists will monitor session duration, goals set, and indication if aerobic physical activity was discussed.

h. Data and Specimen Banking

NA

i. Statistical Analysis

Descriptive statistics will be used to describe baseline characteristics, establish recruitment and retention rates, and examine intervention intensity (session frequency, duration, and fidelity) and patient and therapist satisfaction. Mixed ANOVA or ANCOVAs, if appropriate adjustments are required based on baseline characteristics, will examine the changes in physical activity levels (MVPA/week, steps/day), and pain (PROMIS and WOMAC) across time between PATH and PATH-12. Additionally, differences between PATH and PATH-12 in physical function (chair stands, Timed Up and Go, 6-minute walk) will be examined at 12 weeks. Although the proposed study may not be powered to detect significant differences, the results will allow us to collect feasibility and acceptability data, refine the intervention, if necessary, and determine effect sizes for future grant submissions.

j. Data Management

All surveys will be administered either on paper or online via REDCap (secure, web application for building and managing online surveys and databases – managed by the University of South Carolina). Paper surveys will be stored in a locked filing cabinet at Palmetto Health-USC Orthopedic Center or the TecHealth Center at University of South Carolina. All computer files will be password protected. Only the study team will have access to the data.

k. Confidentiality

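### Aim 2 promises an effect on change in physical function, but the analysis gives only a 12-week difference on tests with no baseline and names no analysis for PROMIS Mobility, collected at both visits

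*Combined protocol and SAP*

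**What the plan says.** Section 3, Aim 2, is to examine the effect of the intervention "on the changes in physical activity, physical function, and pain in TKR patients".

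Section 7f (Secondary Outcomes) defines the function domain by performance tests: "Physical function measures will include the chair stand, timed up and go, and 6-minute walk test". The opening text of 7f fixes their timing: "Only at 12 weeks will participants complete functional tests and the Surgery and Medication Questionnaire". The measures table agrees and shows no baseline mark for any of the three.

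Two patient-reported instruments are scheduled at both visits. The text says "at both assessments, participants will be asked to complete surveys (demographics, brief medical history, KOOS, PROMIS, self-identification", and the table marks baseline and 12 weeks for "Knee Injury and Osteoarthritis Outcome Score (KOOS" and for "PROMIS Pain Intensity, Pain Interference, & Mobility". Mobility is also listed among the patient-reported secondary outcomes: "We will assess pain intensity, pain interference, and mobility". KOOS has no entry in the outcome descriptions.

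Section 7i plans change-over-time models for MVPA per week, steps per day and pain, with PROMIS and WOMAC given as the pain measures. For function it says only that "differences between PATH and PATH-12 in physical function (chair stands, Timed Up and Go, 6-minute walk) will be examined at 12 weeks". ANCOVA is offered in place of mixed ANOVA if baseline characteristics call for adjustment. That provision sits in the sentence on the change outcomes and names no covariate.

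**The concern.** Aim 2 has three components, each framed as change. Activity and pain get a change analysis; function does not, because the measures chosen for it have no starting value. The score that could supply one, PROMIS Mobility, is collected and listed as an outcome, but no analysis is named for it.

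Two things are at stake. First, the trial would report nothing on change in function, although the aim promises it and section 7i says the results will supply effect sizes for future grant submissions. Second, the 12-week comparison of the tests would forgo a baseline covariate that is already being collected. Patients enter at any time up to 2 months after surgery (section 7b), so starting function will vary. Therapists identify candidates (sections 4 and 7a) at sites that are already allocated to a condition for that phase (section 7g), so the arms could differ at entry. The tests themselves offer no baseline on which to see this.

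**Working it through.** The documents give no power, effect size, standard deviation or correlation for this point, so there is no figure of the plan's own to reproduce. The main check is a side-by-side reading of sections 7f and 7i.

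| Measure | Baseline | 12 weeks | Described as an outcome | Analysis named in 7i |
|---|---|---|---|---|
| MVPA, steps | yes | yes | yes | change across time |
| PROMIS pain scores | yes | yes | yes | change across time |
| WOMAC | yes | yes | yes (pain and stiffness) | change across time, as pain |
| PROMIS Mobility | yes | yes | yes | none |
| KOOS | yes | yes | no | none |
| Chair stands, Timed Up and Go, 6-minute walk | no | yes | yes (physical function) | 12-week difference |

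None of the three function tests has a baseline, so change cannot be computed for any of them. WOMAC, as described here, covers pain and stiffness and does not fill the gap. Mobility is the one described secondary outcome on the function side with both time points.

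**Illustration of the precision gain (assumed inputs).** Adjusting a 12-week outcome for a baseline covariate that correlates r with it multiplies residual variance by 1 − r². The assumed range is r = 0.3 to 0.5, for a self-reported score predicting a performance test.

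- r = 0.3: 1 − 0.09 = 0.91, a 9% reduction.
- r = 0.5: 1 − 0.25 = 0.75, a 25% reduction.

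For scale, take the planned 50 patients split equally (25 per arm, an assumption), two-sided alpha 0.05, 80% power and a normal approximation, ignoring clustering and dropout. The detectable standardised difference is (1.960 + 0.842) × √(2/25) × √(1 − r²).

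- No covariate: 2.802 × 0.283 = 0.79 SD.
- r = 0.3: 0.792 × √0.91 = 0.76 SD.
- r = 0.5: 0.792 × √0.75 = 0.69 SD.

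Put another way, 50 adjusted patients carry the information of 50/0.91 ≈ 55 to 50/0.75 ≈ 67 unadjusted ones. Clustering by site would raise all three detectable differences. The documents do not give the number of sites, so that effect is not quantified.

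**The case against.** Several points on the other side are fair.

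- A randomised comparison at 12 weeks can estimate an intervention effect without a baseline, and section 7i already calls the function analysis a difference at 12 weeks. This stands. The effect estimated is on 12-week performance, so the mismatch is with the wording of Aim 2.
- The plan does not commit to an unadjusted test. ANCOVA is allowed conditionally, and the function sentence names no method. This also stands, but a conditional provision attached to other outcomes, with no covariate named, does not pre-specify adjustment here.
- Naming PROMIS without its domains could be shorthand that includes Mobility. That is possible, but the label in 7i is pain, and Mobility is not a pain score.
- The documents never say that KOOS measures function, nor which of its scores would be used. This stands, and the point rests on Mobility alone.
- Aim 2 is secondary, and section 7i says the study may not be powered to detect differences. This limits the weight of the point.

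A reader might go further and infer that the 12-week comparison is biased because few sites are randomised and arms may start at different levels. The documents do not support that. They give no number of sites, and under section 7g each site delivers both conditions in turn, so stable site differences partly offset across arms. Chance imbalance is not bias under randomisation, and any bias figure would need a baseline gap and a correlation that the documents do not provide. What remains is a possibility of differential selection, because patients are identified after sites are allocated.

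**Conclusion.** The point holds as a mismatch between aim and analysis with a free remedy. Followed as written, the plan yields an effect on 12-week performance and no result on change in function, although Mobility is measured at both visits. It would be too strong to say that function goes unexamined or that the planned comparison is invalid.

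The benefit of adjustment is mainly precision: a 9% to 25% lower residual variance for the performance tests, resting wholly on the assumed correlation of 0.3 to 0.5. Adjustment for baseline Mobility also gives some protection against differences in starting function. That protection is only partial, because a self-reported score is a proxy for performance. With feasibility and acceptability as the primary endpoint, the importance is modest.

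**What to change.** 1. In section 7i, add PROMIS Mobility to the baseline-to-12-week models as the change-in-function outcome for Aim 2. Use KOOS for this purpose only if a specific score is named; otherwise state what KOOS is collected for.
2. Pre-specify baseline PROMIS Mobility as a covariate in the 12-week comparisons of chair stands, Timed Up and Go and 6-minute walk, whether or not the arms look balanced at baseline.
3. Reword Aim 2 so that the performance tests are 12-week differences and the term change is kept for outcomes measured at both visits.

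The cost is wording in sections 3 and 7i. No visit, instrument or patient burden is added, because Mobility is already scheduled at both assessments. The changes should be made before outcome data are examined by arm.

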PATH-12 (control). Patients randomized to receive PATH-12 will undergo the standard physical therapy following TKR. The study will not change any treatment patients typically receive and instead will just document how long sessions occur and if any aerobic activity goals were set. In addition to the standard physical therapy received and to enhance retention in the study, all participants who receive PATH-12 will be given a brief physical activity coaching session led by a trained USC research staff member at 12 weeks following the completion of the assessment. Participants will receive all materials

provided to PATH and the session is expected to last approximately 1 hour. In the event this cannot be completed in-person, it will be completed over the telephone.

PATH. Patients randomized to receive PATH will undergo the standard physical therapy following TKR. In addition, physical therapists will briefly discuss lifestyle and moderate-to-vigorous physical intensity activity at each session. At least once/week, physical therapists will help patients set a SMART (Specific, measurable, attainable, realistic, timely) goal related to overall aerobic physical activity and identify strategies that will help them achieve their goal. Physical therapists will use motivational interviewing techniques and check in on patients' progress towards goals at each session. Physical therapists will be encouraged to engage in physical activity coaching and goal setting during down time while patients are completing aerobic warm up, rehabilitation exercises, or during ice, manual therapy, neuromuscular electrical stimulation, or scar management to ensure these discussions do not add additional time to the regular therapy session.

Intervention Data Collection. Physical therapists for both randomized conditions will document the session start and end times as well as any goals that are set during the sessions. Physical therapists can document the session information on a paper form

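### The protocol does not fix whether control patients are coached before or after the 12-week activity-monitoring week, so coaching may overlap their only follow-up activity measurement

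*Combined protocol and SAP*

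**What the plan says.** **Control coaching (section 7g, Randomized Conditions, PATH-12).** Controls "will be given a brief physical activity coaching session led by a trained USC research staff member at 12 weeks following the completion of the" 12-week assessment. Controls receive everything "provided to PATH and the session is expected to last approximately 1 hour". In person is the default: "In the event this cannot be completed in-person, it will be completed over the telephone". The stated purpose is to help retention.

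**Monitoring (section 7f, Study Endpoints).** "Participants will also be given an Actigraph Link accelerometer and ActivPAL monitor to wear for 7 days at each assessment". On hand-over: "These monitors will be provided at the in-person assessment or mailed to the participants". On return: "At the end of the 7 days, these monitors will be returned to the PT clinic", or a prepaid envelope is used. No mailing date relative to the visit is given.

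**Description of the wear week (section 7f, Secondary Outcomes).** For each monitor, patients keep a log; for the Actigraph it shows "times the accelerometer was worn and taken off over the 7-day assessment period".

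**Use of the data.** Activity is measured at baseline and 12 weeks only. Section 7i compares change in MVPA per week and steps per day between the arms, and intends the results to supply effect sizes for later grant applications. Sedentary time is a secondary outcome in 7f but is not named in Aim 2 or in the 7i analyses. The primary endpoint is feasibility and acceptability.

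**The concern.** The control session delivers activity coaching, which is what PATH adds to standard therapy. Section 7g randomizes sites rather than patients to avoid contamination, and its Treatment Fidelity paragraph gives activity goal setting with a PATH-12 patient as an example of contamination. If a site finishes the surveys and function tests, hands over the monitors and then coaches the patient at the same visit, the control arm's follow-up week becomes a coached week. PATH patients have no matching session at that point, so the exposure falls on one arm only.

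There is one follow-up wear week. Adjusting for baseline characteristics, site or phase would not recover the uncoached control value. The overlap could also go unnoticed: the session forms and fidelity checklists cover the physical therapists' sessions, whereas research staff give the control coaching, and the protocol does not require its date to be recorded.

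**Working it through.** The documents give no power, target effect or sample-size calculation for the activity outcomes, so there is no stated figure to reproduce. The check is mainly one of reading.

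**1. Does the assessment include the wear week?**

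- *For:* the 7f outcome descriptions place monitor wear within the assessments and call the 7 days an assessment period. The 7f schedule lists Actigraph and ActivPAL as 12-week measures. On this reading, coaching follows wear and there is no problem.
- *Against:* 7f also uses the term in-person assessment for the visit at which monitors are given out. It further requires the baseline assessment to be completed before the second outpatient session. The background section puts therapy at 2-3 sessions a week, so the average gap between sessions is 7/3 = 2.3 to 7/2 = 3.5 days. Seven days of wear would not normally fit into that gap, and section 7a allows consent as late as the second appointment. At baseline, then, an assessment can count as completed while the monitors are still being worn.

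The same word carries two meanings, and only one of them protects the outcome.

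**2. Which sequences does the text allow?**

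| Monitors | Coaching | Outcome week in controls |
|---|---|---|
| Handed over at the visit | Same visit | Coached throughout |
| Handed over at the visit | By telephone during wear | Partly coached |
| Handed over at the visit | At or after monitor return | Uncoached |
| Mailed and worn before the visit | At the visit | Uncoached |
| Mailed and worn after the visit | At the visit | Coached throughout |

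No sentence rules out any of these rows.

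**3. How large could the effect be? (illustration only)**

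Let *f* be the share of controls coached before or during wear, and *g* the fraction of the PATH effect that one session produces in that week. Then

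observed difference = true difference × (1 − f·g).

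Neither *f* nor *g* is in the documents. For scale I use the 12-week steps/day SDs in Table 1 (Preliminary Studies), 1687.8 (n=6) and 1653.2 (n=7), from an earlier weight-loss pilot:

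pooled SD = √[(5 × 1687.8² + 6 × 1653.2²)/11] = 1669.

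Power is the normal approximation Φ(d/(1669 × √(2/25)) − 1.96), where d is the observed difference. It assumes 25 per arm and two-sided 5%, and ignores clustering. The 25s in the protocol are per phase, so 25 per arm is itself an assumption.

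| Assumed true difference, steps/day | f | g | Observed | In SDs | Power |
|---|---|---|---|---|---|
| 1000 | 0 | – | 1000 | 0.60 | 0.56 |
| 1000 | 0.25 | 0.25 | 938 | 0.56 | 0.51 |
| 1000 | 0.5 | 0.5 | 750 | 0.45 | 0.36 |
| 1000 | 1 | 0.5 | 500 | 0.30 | 0.18 |
| 1500 | 0 | – | 1500 | 0.90 | 0.89 |
| 1500 | 0.5 | 0.5 | 1125 | 0.67 | 0.66 |
| 1500 | 1 | 0.5 | 750 | 0.45 | 0.36 |

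The effect size carried forward matters more here than power. Required sample size varies as 1/(effect)². A later trial without the overlap, but sized on the diluted estimate, would be 1/0.75² = 1.8 times as large as needed at f = g = 0.5, and 1/0.5² = 4 times at f = 1, g = 0.5.

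**The case against.** The strongest reply is that the existing wording already gives the right order. Coaching follows completion of the assessment, the outcome descriptions treat the 7 wear days as part of the assessment, and an assessment with a 7-day component is not complete on day 0. Coaching after wear is also practical as written, because monitors may be brought back to the clinic and the telephone is allowed. This is a fair reading and may be what the investigators intend. It does not settle the matter, because the baseline rule in 7f uses completion in the narrower sense and nothing ties coaching or materials to the end of wear.

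A reader might infer something stronger: that the protocol has controls coached at the 12-week visit, with monitoring always starting there, so that all 7 outcome days are contaminated. The documents do not say this. Same-visit coaching is an inference from the in-person default, and mailed monitors have no stated date and could be worn before the visit.

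Three other parts of the objection stand. The affected outcomes are secondary, in a pilot that says it may not be powered. The fractions *f* and *g* are assumed, and the SD comes from 13 patients. Taking *g* = 1 would equate one session with a programme raised at every therapy visit, so it is an extreme bound.

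**Conclusion.** The concern holds as an undefined sequence, not as a stated error. The protocol permits control patients to be coached, with all PATH materials in hand, before or during their only follow-up wear week. If that occurs and coaching raises activity, the estimates for MVPA per week and steps per day, and also ActivPAL sedentary time, are biased toward no difference. The loss is the proportion f·g of the true effect. It could be nil if sites already wait for the monitors, or substantial if coaching at hand-over is routine; the documents do not allow a choice between these.

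The primary feasibility and acceptability endpoint is unaffected, as are function tests and surveys completed before coaching. Surveys completed online after coaching could be affected. This is a cheap improvement and falls short of a must-fix. I am confident that the order is undefined, and much less so about how often overlap would happen.

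**What to change.** In section 7g, PATH-12, replace the timing phrase with wording such as: *PATH-12 coaching and all PATH materials are given only after the 12-week Actigraph and ActivPAL have been worn for 7 days and returned.* The session can take place when monitors are returned to the clinic, or by telephone, which is already permitted. Record the coaching date and the wear dates for every control patient.

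Do not discard control wear days that fall on or after coaching in the main analysis. Such a rule would remove data from one arm only. It could delete a patient's whole week, and partial weeks would make total weekly MVPA non-comparable between arms. If overlap occurs, report how many patients and days are involved and examine it in a sensitivity analysis.

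The cost is one sentence and two recorded items. Control coaching moves about 1-2 weeks later and more sessions may be by telephone. No patients or staff are added, and no visit beyond the monitor return already provided for. Holding the session until monitors are back also fits its retention purpose, since it gives controls a reason to return them.
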